5.10.2 Handling of Missing Primary Endpoints

As noted above, it is expected to be able to evaluate NICCE in all patients based on the *a priori* specification for this endpoint. If there are any patients with missing primary endpoints, these subjects will be treated as NICCE and CPPE failures in primary analyses and tipping point sensitivity analyses will be conducted. In these analyses, missing values in each group are separately assumed to be either successes or failures. Treatment group differences are computed

based on all possible combinations of assigning success or failure to NICCE to the patients in the two groups. For example, one scenario will be that all missing Reltecimod observations are failures and all missing placebo observations are successes. The next scenario would have one success and the remaining missing values as failure for Reltecimod and all missing placebo outcomes as successes, etc. For each scenario, the hypothetical p-value for testing the primary effectiveness hypothesis will be determined. If there is more than a very few missing values, these results will be plotted using a dot plot with the number of missings assumed as failures for Reltecimod on the x-axis and the number of missing assumed as failures for placebo on the Y-axis. The dots will be color coded to indicate whether or not the primary statistical conclusion changes under each individual scenario. If the fraction of scenarios in which the statistical conclusion changes is small, the primary results will have been shown to be robust against assumptions concerning missingness. If there is more than a small amount of missing data, multiple imputation of missing endpoints may be performed in additional supporting analyses using the SAS procedures, Proc MI and Proc MI Analyze. However, this is not expected to be necessary.

5.10.3 Mixed Model Repeated Measures

The use of MMRM is another method used to address missing data and is considered an optimal approach in many settings. The use of MMRM results in implicit imputations for missing data which are valid under missing at random (MAR), a more general set of assumptions than 'missing completely at random (MCAR)'. For these analyses, there will be implicit imputation of expected mSOFA after patient death. Methods assuming Not Missing at Random (NMAR) require extensive modelling and sensitivity analyses regarding inherently untestable assumptions concerning the missingness mechanism; and will not be used in these analyses.

5.11 Prior and Concomitant Medication

Medication start and stop dates will be compared to the date of first dose of study medication to allow medications to be classified as either prior or concomitant and will be recorded up to Day 28 If the start and/or stop dates of medications are missing or partially missing, the dates will be compared as far as possible with the date of administration of study drug. Medications starting after the completion/withdrawal date will not be classified or summarized.

- Medications that start and stop prior to the date of first dose of study medication will be classified as prior only.
- A medication will be regarded as concomitant if it started on or after the date of first dose of study treatment.
- A medication will also be regarded concomitant if:
 - it started prior to date of first dose of study treatment but was ongoing at the time of the first dose of study treatment.
 - the start date of medication is completely unknown.

Medications are coded prior to delivery of the validated clinical data base. The following describes this process.

Drugs are coded to the WHO Drug entry that best (most accurately and specifically) represents the reported term. If a reported term is a trade name, then it will generally be coded to the trade

name entry in WHO Drug that contains the correct active ingredients for that trade name. If a reported term is a generic name, then it will generally be coded to the generic entry in WHO Drug with that ingredient or combination of ingredients.

A WHO Drug entry may have one or more ATC (Anatomic-Therapeutic-Chemical) codes assigned to it within the dictionary. If a WHO Drug entry has only one ATC code, then that ATC code is additionally returned for that WHO Drug entry. If a WHO Drug entry has more than one ATC code assigned, then a single ATC code is selected based on the most common usage for the drug and the selected ATC code is additionally returned for the WHO Drug entry.

5.12 Deviations from the Original Statistical Plan

Any deviations from the original statistical plan will be described and justified in the final report.

6 Safety Analysis

The safety measures for this study are AEs, clinical safety laboratory, physical exam, vital signs, ECG (screening day 0 and day 1 post drug) and SAEs including determination of survival through Day 90. The safety profiles will be compared between Reltecimod and placebo groups using descriptive statistics as appropriate for continuous and categorical safety variables.

6.1 Adverse Events

AEs will be classified according to system organ class and preferred term and summarized by counts and percentages separately for those recorded on day 0 (prior to drug administration) and for treatment emergent adverse events (TEAEs) defined as those with onset on day 1 or later. TEASs will also be summarized by relationship to study drug, severity, and whether they are serious.

6.2 Laboratory Values

6.2.1 Description of Value Over Time

Laboratory values over time including blood chemistry and hematology will be summarized using descriptive statistics and compared between treatment groups. Values over time and changes over time will be summarized.

6.2.2 Laboratory Shift Tables

The presence of clinically significant changes in laboratory values will be further evaluated using shift tables for blood chemistry and blood hematology changes from screening to Day 7 and from screening to Day 14. These tables will summarize the numbers and percentages of patients that went from a lab value in the normative range at screening to one that is in the higher than normal range or lower than normal range.

6.2.3 Treatment of Clinical Laboratory Abnormalities

Deterioration as compared to baseline in protocol mandated laboratory values, vital signs and other safety variables will only be reported as AEs only if they fulfill any of the SAE criteria or are the reason for discontinuation of treatment with the investigational medical product. However, the Investigator may record such findings as an AE at his/her discretion in addition to completing an unscheduled laboratory/vital signs eCRF with the information on the clinically significant test abnormality. If a deterioration in a laboratory value/vital sign is associated with clinical signs and symptoms, the sign/symptom will be reported as an AE and the associated laboratory result/vital sign will be considered as additional information. Any new or aggravated clinically relevant abnormal medical finding at a PE, dermal examination or lung auscultation as compared with the baseline assessment will be reported as an AE. Clinically relevant deterioration in unscheduled assessments of laboratory/vital signs/ECG parameters should be reported on additional eCRF pages.

Wherever possible, the reporting Investigator uses the higher level medical concept, rather than the laboratory term (e.g., anemia versus low hemoglobin value).

Additionally, for blood chemistry and blood hematology, results at each visit will be summarized according the frequency of "Critical High", "Above", "Within", "Below", and "Critical Low" results.

6.3 Electrocardiogram

ECG data will be reviewed by the principal investigator and by an external independent and blinded cardiologist. The blinded core lab evaluation is referred to as "Central Reader". Results will be summarized for the investigator based and central reader based results.

Electrocardiogram results from screening, immediately post drug administration, 4-6 hours post drug administration, and 12-24 hours post drug administration; and changes from screening will be summarized using the As Treated (Safety) Analysis set. Descriptive statistics will include N, mean, median, standard deviation, minimum, and maximum values. Electrocardiogram characteristics to be summarized include heart rate, RR interval, PR interval, QRS complex time, QT interval, and the QTc interval. The results from the central reader will include the QTcB and QTcF intervals.

ECG abnormalities observed during a study will be encompassed under a reported adverse event describing a clinical syndrome. In these cases, the ECG abnormality itself does not need to be recorded as an adverse event.

Similar to that described for laboratory abnormalities, deterioration in baseline ECG parameters as compared to baseline should only be reported as AEs if they fulfil any of the SAE criteria or are the reason for discontinuation of treatment with the investigational medical product. However, the Investigator may record such findings as an AE at his/her discretion in addition to completing an unscheduled ECG eCRF with the information on the clinically significant test abnormality.

6.4 Physical Exams

Results from physical exams will be tabulated for the Safety Anaysis Set on screening day 0 ('Normal' vs 'Abnormal') as well as for days 3, 7, and 14. The following systems will be assessed: abdomen; cardiovascular; extremities; eyes, ears, nose, and throat; general appearance; head and neck; lymph nodes; neuorlogical; respiratory; and skin. On days 3, 7, and 14, patients will be categorized according to 'Normal', 'Abnormal, improved or same as screening', 'Abnormal, new or aggrevated' and 'Not done'. These data will be summarized as shift tables from the screening visit with results descriptively compared between the Reltecimod and Placebo drug groups.

6.5 Vital Signs

Vital signs include height, weight, BMI, temperature, systolic BP, diastolic BP, MAP, respiration rate, and heart rate. Height and BMI will be summarized at the screening visit by treatment group. The remaining vital sign variables will be summarized as values and as changes from screening across time (day 1, day 2, day 3, day 7, day 10, day 14, day 21, and day 28), separately by treatment group using N, mean, SD, median, minimim, and maximum values. Vital signs will be summarized for the As Treated (Safety) Analysis Set.

7 Presentation of Enrollment and Baseline Characteristics

7.1 Numbers of Patients by Analysis Set

Table 14.1.1.1 summarizes the numbers of patients screened, randomized, and in each analysis set (ITT, As Treated, mITT, and Per Protocol).

Table 14.1.1.2 summarizes the numbers of patients in each analysis set by treatment group and site.

Table 14.1.1.3 summarizes the numbers of patients by site, treatment group, and randomization stratum in the As Treated (Safety) analysis set. Randomization strata are defined as follows:

$$(+,+) = (mSOFA>4, Fournier's)$$
 $(+,-) = (mSOFA>4, No Fournier's)$

$$(-,+) = (mSOFA=3-4, Fournier's)$$
 $(-,-) = (mSOFA=3-4, No Fournier's)$

Tables 14.1.1.4 and 14.1.1.5 provide the same summaries for the mITT and Per Protocol analysis sets, respectively. Totals across all sites will be provided for both of these tables.

7.2 Demographic and Baseline Disease Characteristics of Cohorts

Demographic and baseline characteristics of each analysis set are summarized in Tables 14.1.2.1, 14.1.2.2, and 14.1.2.3, and 14.1.2.4 for the ITT, AT (safety), mITT, and Per Protocol analysis sets, respectively.

Tables 14.1.3.1, 14.1.3.2, 14.1.3.3, and 14.1.3.3 summarize the numbers of patients overall and by treatment group, age category, and gender, for the ITT, AT, mITT, Per Protocol analysis sets respectively.

7.3 Baseline Microbiology

Table 14.1.3.5 summarizes pathogens in tissue samples and blood cultures, overall and by treatment group. The data used are based on verbatim text.

7.4 Prior and Concomitant Medication

Prior and concomitant medication, lifetime and current medications, will be summarized for the All Treated (Safety) analysis set as are all Safety endpoints.

Table 14.1.4.1 will summarize the numbers (%) of patients with prior ancillary (e.g., non-antimicrobial or non-immunosuppressant) medications by category and by specific medication, overall and by treatment group.

Table 14.1.4.2 will present same for antimicrobial and immunosuppressant medications.

Table 14.1.4.3 will summarize the numbers (%) of patients with concomitant ancillary medications by category and by specific medication by treatment group.

Table 14.1.4.4 will present same for antimicrobial and immunosuppressant medications.

7.5 Medical History

Table 14.1.5.1 will summarize the numbers and percentages of patients that experienced prior medical conditions during their lifetime by body system and specific medical condition, overall and by treatment group.

Table 14.1.5.2 will summarize the numbers and percentages of patients with ongoing medical conditions by body system and specific medical condition by treatment group.

7.6 Presentation of NSTI

A summary of factors related to presentation and diagnosis of NSTI will be provided in Table 14.1.6.1. Table 14.1.6.2 will list extensions of NSTI within initial debridement surgery categories.

7.7 Drug Administration and Timing

Day 1 information regarding time from clinical diagnosis to drug allocation, drug administration time point (during or after surgery), and the actual volume of drug infused will be described in Table 14.1.7.1. Drug exposure will be summarized in Table 14.1.7.2.

7.8 Patient Disposition and End of Study Status

Table 14.1.8.1 summarizes patient disposition and end of study status by treatment group based on the As Treated (Safety) Analysis Set.

8 Presentation of Efficacy Results

8.1 Primary and Conditional Co-Primary Endpoint in mITT Analysis Set

The numbers and percentages of patients in the mITT analysis for each group meeting the primary efficacy endpoint (NICCE) and the conditional co-primary efficacy endpoint (CCPE) are summarized in Tables 14.2.1.1 and 14.2.1.2, respectively. These tables include the statistical significance of the group difference based on unadjusted two-sided chi-square statistics. Study success requires $p \le 0.01$ for the primary endpoint and $p \le 0.05$ for the conditional co-primary endpoint. These tables also provide the estimated treatment group differences for both endpoints as well as the 99% confidence interval for the primary endpoint and the 95% confidence interval for the conditional co-primary endpoint. Figures 1 and 2 will be bar charts that illustrate these primary study results. Figures 3 and 4 will be forest plots that summarize the point estimates and confidence intervals of the endpoints and their components.

Tables 14.2.1.1 and 14.2.1.2 also summarize the components of the NICCE and the conditional co-primary endpoint. P-values are provided for descriptive purposes only since there were no *a priori* hypotheses concerning the components, other than they would generally show group differences in the same direction. 95% confidence intervals are provided in order to facilitate an evaluation of the statistical precision in the estimated group differences.

The components of NICCE are:

- Alive at Day 28
- <=3 debridements through Day 14
- No amputation beyond first debridement
- mSOFA score of <=1 at Day 14
- Reduction of >= 3 between baseline and Day 14 in mSOFA

The components of the conditional co-primary endpoint (CCPE) are:

- Alive at Day 28
- <=3 debridements through Day 14
- No amputation beyond first debridement

8.2 Primary and Co-Primary Endpoint in Per Protocol Analysis Set

Tables 14.2.1.3 and 14.2.1.4 repeat the analyses above in the Per Protocol analysis set.

8.3 Evaluation of Site Heterogeneity in Primary Endpoint Treatment Effects

Table 14.2.1.5 provides comparisons of the percentages of patients achieving NICCE by site and treatment group. Site-to-site heterogeneity will be evaluated with these data using a random effects 'meta-analysis approach as described in Section 4.3 above. Table 14.2.1.6 provides the same summary for the conditional co-primary endpoint.

8.4 Evaluation of Stratification Factors

Table 14.2.1.7.1 summarizes the numbers and percentages of subjects achieving the NICCE within each level of the randomized stratification. The generalized linear model stratum adjusted risk difference, 99% confidence interval, and the adjusted p-value is presented for comparison to primary unadjusted results. A test for stratum by treatment group interaction will also be presented.

Table 14.2.1.7.2 provides the same analysis but based on the true stratification status. If there are no subjects that were placed in the incorrect stratum, this table will not be produced.

8.5 Sensitivity Analysis Removing the Reduction in mSOFA Component

Table 14.2.1.8 provides a sensitivity analysis for the primary NICCE endpoint. In this analysis, the requirement that there be at least a 3 point reduction in mSOFA from screening to Day 14 is removed. This was the original formulation of the NICCE endpoint before FDA requested that that the reduction component be included for this trial.

8.6 Distribution of mSOFA scores Over Time

Table 14.2.2.1 summarizes mSOFA and its 5 components over time, from screening to Day 28. Since bilirubin is collected only at screening and at Day 7 and 14, observed SOFA total scores will also be summarized at these three timepoints.

Table 14.2.2.2 provides the same summary after application of last-value-carried forward (LOCF) to Day 14. LOCF was not applied after patient death or for missing Day 21 or Day 28 mSOFA.

Table 14.2.2.3 summarizes changes from Day 0 in mSOFA and in each of its components to Days 1, 2, 3, 7, 10, 14, 21, and 28 without applying LOCF.

Table 14.2.2.4 provides the same summary after application of LOCF to Day 14. This table only summarizes mSOFA to Day 14 because there was no LOCF imputation for missing mSOFA after Day 14 and so the results for Days 21 and 28 are identical to the table summarizing mSOFA without LOCF.

Tables 14.2.2.5 and 14.2.2.6 provides the same summaries for observed and LOCF imputed mSOFA and components to Days 28 and 14, respectively, but for changes from Day 1 rather than Day 0.

The data displayed in Tables 14.2.2.1 to 14.2.2.6 will be graphically displayed in line plots comparing between treatment groups using line plot (Figures 5 to 10) and box and whiskers plots (Figures 11 to 14).

Table 14.2.2.7 will summarize mSOFA and organ specific values at screening, 16 - 24 hours post dose, and changes from screening to 16 - 24 hours post dose.

Table 14.2.2.8 will summarize mSOFA without the Glasgow Coma Score and without the Glasgow Coma Score Among Patients on Ventilation and Medications Affecting GCS to Day 28.

8.7 Time to resolution of mSOFA score to ≤ 1

Life tables for time to resolution of mSOFA score ≤ 1 will be provided in Tables 14.2.3.1 and 14.2.3.2 for the 0.50 mg/kg and placebo treated groups, respectively, to Day 14. Comparative Kaplan-Meier survival curves will be provided in Figure 15.

For these analyses, patients who die prior to Day 14 will be considered censored at one day past Day 14 and assumed to have never achieved mSOFA \leq 1. Log rank statistic will be used to assess if the distributions of times to symptom resolution differ between treatment groups.

These analyses will be repeated using follow-up through Day 28 in Tables 14.2.3.3 and 14.2.3.4 and in Figure 16. For these analyses, patients who die after Day 14 but prior to Day 28 will be evaluated for meeting the mSOFA≤1 and will be considered a success in these analyses if they achieve mSOFA≤1 (prior to their post Day 14 death).

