2.4 Sample Size Justification

2.4.1 Primary Endpoint

This trial will enroll 290 subjects that will be randomized in a ratio of 1:1 to either Reltecimod 0.50 mg/kg (n=145) or placebo (n=145), each in addition to standard of care. Sample size analysis was performed assuming that all patients will be evaluable for the primary endpoint. This assumption is justified on the basis of results from the Phase 2a trial and the Retrospective Study in which all patients were evaluable in terms of the definitions used to construct the NICCE endpoint.

The primary efficacy hypothesis will be tested using an unadjusted χ^2 statistic with an α =0.01 two-sided significance level. Statistical power was computed for a range of expected treatment group differences supported by the results of the preliminary studies noted above. For expected treatment group differences of 0.30, 0.25, and 0.20, statistical power will be 99%, 95.9%, and 80.2%, respectively. These power determinations were conservatively made assuming an average success rate between treatment groups of 0.5. In this way power estimates are applicable across the range of expected response rates; but may be conservative in some cases.

The use of NICCE and this range of expected treatment effects is supported by preliminary studies as summarized in the following table.

	Percentage Achieving NICCE	(n/N)
Phase 2a (mSOFA≥3) Reltecimod 0.50 mg/kg	71.4%	(5/7)
Phase 2a (mSOFA≥3) Placebo	20.0%	(1/5)
Retrospective Study (mSOFA≥3)	30.4%	(21/69)

In the Phase 2a trial, 71.4% (5/7) patients with baseline mSOFA≥3 treated with Reltecimod (at a dose of 0.50 mg/kg) achieved NICCE. In contrast, only 20% (1/5) of placebo patients with baseline mSOFA≥3 achieved NICCE, a difference of 51.4%. The Retrospective Study provides further support for the untreated response rate. Among 69 patients with baseline mSOFA≥3, 30.4% (21/69) achieved NICCE, a difference of 41.0% relative to Phase 2a patients in the 0.50 mg/kg treated group presenting with screening mSOFA≥3.

Given the selected sample sizes, if the observed differences in this study happen to be equal to 35%, 25%, or 20% (centered about 50%), then the corresponding 2-sided p-values will be

p<0.0001, p<0.0001, and p=0.0007, respectively. The observed difference will need to be larger than about 16% (e.g., 58% vs 42%) for p \le 0.01 (again assuming that the average success rate between groups is 50%).

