5.2.3 Time to Organ Dysfunction Resolution

Time to organ dysfunction resolution will be evaluated as a time-to-event endpoint. This will be assessed in descriptive analyses using survival and life-table methods and calculated from time of drug administration. Organ dysfunction resolution will be defined as mSOFA score ≤ 1 . Two analyses will be performed. The first corresponds to the primary efficacy endpoint and evaluates time to mSOFA score ≤ 1 censoring at Day 14. The second extends the follow-up range to Day 28 using available observed mSOFA.

¹⁰ Kaplan EL and Meier P. Nonparametric estimation from incomplete observations, Journal of the American Statistical Association 1959, 53:457-481.

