5.7 Descriptive Analyses of Additional Secondary Endpoints

Additional secondary endpoints have been specified from several domains including individual components of the primary composite endpoint (NICCE), time to resolution of organ dysfunction, critical care and hospital stay parameters (ICU and ICU-free days, ventilator days and -free days, vasopressor days and -free days, hospital LOS), clinical local parameters (debridement history variables), and clinical systemic parameters (mSOFA over time, incidence and recovery from AKI). Analyses for these endpoints will generally be descriptive, with emphasis on characterizing clinical effect sizes¹⁵. Nominal p-values will be presented in some cases as an aid to interpretation but with no adjustment for multiplicity. Categorical outcomes will be summarized using counts and percentages with nominal p-values determined through chi-square or exact methods. Critical care and hospital stay endpoints will be compared using non-parametric approaches including using concordance statistics (c-stat) to characterize clinical effect size and Wilcoxon rank sum tests to determine nominal statistical significance. The c-stat is the probability that a randomly selected patient treated with Reltecimod has a better (e.g., greater number of free-days) than a randomly selection patient treatment with placebo. Methods appropriate for time-to-event endpoints including survival and life-table methods will be used for time-to-organ dysfunction resolution endpoints. Additional analyses of mSOFA over time will employ methods appropriate for longitudinal data. For these analyses, statistical testing and estimation will be based on a Mixed Model Repeated Measures (MMRM)¹⁶.

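### SAP 8.7 extends the time-to-resolution analysis to Day 28 without moving the Day 15 censoring of early deaths, so the Day 28 Kaplan-Meier estimate as written overstates resolution

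*SAP*

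**What the plan says.** SAP 5.2.3 defines resolution of organ dysfunction as mSOFA ≤1 and plans two analyses, one censored at Day 14 and one longer: "The second extends the follow-up range to Day 28 using available observed mSOFA". It gives no rule for deaths in either.

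The death rules are in SAP 8.7. For the Day 14 life tables (Tables 14.2.3.1 and 14.2.3.2, Figure 15), "patients who die prior to Day 14 will be considered censored at one day past Day 14", and the same sentence assumes that these patients never reached the threshold. The comparison is by log-rank: "Log rank statistic will be used to assess if the distributions of times to symptom resolution differ between treatment groups".

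The Day 28 version follows: "These analyses will be repeated using follow-up through Day 28 in Tables 14.2.3.3 and 14.2.3.4 and in Figure 16". One death rule is added: "patients who die after Day 14 but prior to Day 28 will be evaluated for meeting the mSOFA" threshold, and they count as successes if they met it before dying. The section does not give:

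- a new censoring day for deaths before Day 14;
- a censoring time for patients who die unresolved after Day 14;
- a rule for death on Day 14 itself.

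After Day 14, mSOFA is assessed only at Days 21 and 28. SAP 8.6 tabulates changes "to Days 1, 2, 3, 7, 10, 14, 21, and 28 without applying LOCF", and SAP 5.2 rules out carrying total scores forward at those two visits.

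On status, SAP 4.2 lists the Day 28 version among additional secondary endpoints, and SAP 5.7 says of that group: "Analyses for these endpoints will generally be descriptive, with emphasis on characterizing clinical effect sizes". SAP 5.6 makes no attempt to control type 1 error for them. Protocol 2.2 and 7.2 list only the version censored at Day 14.

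**The concern.** Kaplan-Meier treats a censored patient as someone who could still have the event, at the rate seen in those who remain. Censoring the dead one day past a Day 14 horizon does no harm, because they stay in the denominator as non-resolvers until the curve ends. If the same day is kept and the curve runs on to Day 28, they leave before the last two assessments. They are then credited, in effect, with resolving at the survivors' rate, which contradicts the SAP's own assumption that they never resolved.

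SAP 4.3 recognises competing mortality for ventilator, ICU and vasopressor outcomes and uses free days to deal with it. The Day 28 curve would bring the problem back. At stake is the effect size shown in Tables 14.2.3.3 and 14.2.3.4, Figure 16 and the accompanying log-rank comparison.

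**Working it through.** The plan gives no event count, power or expected result for this analysis, so there is no figure of its own to reproduce. The check is on what the stated rule produces.

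**Inputs**

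- Early deaths censored at Day 15: SAP 8.7.
- Resolutions after Day 15 observable only at Days 21 and 28: SAP 8.6.
- Sample size, SAP 2.4.1: "This trial will enroll 290 subjects that will be randomized in a ratio of 1:1", so 145 per arm.
- q, share dead before Day 14 and counted as unresolved: not in the documents; assumed 5–20%. As a guide only, Phase 2 mortality was 20% on placebo and 6.7% at 0.5 mg/kg (Protocol Table 3), not split at Day 14. Protocol 1.1.1 cites up to 17% from the literature.
- h, chance that a patient alive and unresolved at Day 14 resolves by Day 28: not in the documents; assumed 0.3–0.7.
- r, share resolved by Day 14: assumed 0.5 unless stated.
- Deaths after Day 14 and missing late scores are set aside.

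**Formulas**

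- Proportion truly resolved by Day 28: r + h(1 − r − q)
- Kaplan-Meier with early deaths censored at Day 15: 1 − (1 − r)(1 − h) = r + h(1 − r)
- Overstatement: h × q, whatever r is

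**Overstatement in percentage points**

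| | q = 5% | q = 10% | q = 15% | q = 20% |
|---|---|---|---|---|
| h = 0.3 | 1.5 | 3 | 4.5 | 6 |
| h = 0.5 | 2.5 | 5 | 7.5 | 10 |
| h = 0.7 | 3.5 | 7 | 10.5 | 14 |

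**Two arms in whole patients** (72 of 145 resolved by Day 14 in each arm, h = 0.5, q = 6.7% active and 20% placebo)

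- Active: 10 early deaths, 145 − 72 − 10 = 63 alive and unresolved, of whom 32 resolve. True: (72 + 32)/145 = 71.7%. As written: 1 − (73/145)(31/63) = 75.2%.
- Placebo: 29 early deaths, 145 − 72 − 29 = 44 alive and unresolved, of whom 22 resolve. True: (72 + 22)/145 = 64.8%. As written: 1 − (73/145)(22/44) = 74.8%.
- A true difference of 6.9 points appears as 0.4. The log-rank p-value is 0.97 as written, against 0.39 with the dead held to Day 29.

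**Sensitivity of the between-arm difference**

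- r = 0.60 active and 0.40 placebo, same h and q. True: 0.60 + 0.5(0.40 − 0.067) = 76.65% against 0.40 + 0.5(0.60 − 0.20) = 60%, a difference of 16.65 points. As written: 80% against 70%, or 10 points.
- Unequal h: active q = 10%, h = 0.6; placebo q = 15%, h = 0.3; r = 0.5 in both. The overstatement is 6 points on active and 4.5 on placebo, so it is larger in the arm with fewer deaths. The true difference of 74% − 60.5% = 13.5 points appears as 80% − 65% = 15.

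**After the change.** With early deaths kept in the risk set to Day 29, the Kaplan-Meier estimate at Day 28 equals the true proportion in every scenario computed.

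**The case against.** The strongest objection is that Day 15 is never restated for the Day 28 analysis. The rule sits in the paragraph on the Day 14 tables and reaches the longer analysis only because that analysis is a repeat. Since the SAP assumes that early deaths never resolve, one day past the horizon could naturally be read as Day 29. A reader might infer that the sponsor deliberately chose a biased method; the text does not support that. What stands against the objection is that the only day the SAP gives is one day past Day 14, and a programmer following it would use that day.

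The second objection concerns importance, and it stands. The Day 28 version is not a protocol endpoint, carries no alpha and is described as supportive. A reader might infer that the success criterion is at risk; it is not.

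Two further readings are tempting and go too far. One is that the overstatement is always greatest in the arm with more deaths; the unequal-h example shows that this needs similar late resolution among survivors. The other is that a life-saving effect would earn no credit. The difference vanishes only when Day 14 resolution and h are alike in the arms; with r at 0.60 and 0.40, 10 of 16.65 points remain. Survival is also counted in NICCE, the conditional co-primary endpoint, the free-day outcomes and the Day 90 survival curves.

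**Conclusion.** The point holds for the Day 28 analysis as written. Early deaths leave the risk set at Day 15, and the estimate exceeds the proportion actually resolved by h × q: about 1.5 to 14 points over the assumed ranges, neither of which can be narrowed from the documents. Using Phase 2 mortality as q places all of those deaths before Day 14, so the two-arm example is an illustration and not a forecast.

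If h is similar in both arms, the overstatement is larger where early deaths are more frequent. It would then mask a benefit if the drug lowers early mortality and mask a harm if it raises it. Censoring unresolved later deaths at the time of death would add a bias of the same kind, but the SAP does not say that this will be done.

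A separate asymmetry needs a decision: someone who resolves and then dies on Day 10 is a non-event under the early rule, while someone who resolves and then dies on Day 16 is a success. Which to prefer is a choice of endpoint, not part of the bias.

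The consequence is confined to Tables 14.2.3.3 and 14.2.3.4, Figure 16 and their nominal p-value. It is worth correcting because the purpose of this analysis is to show effect size.

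**What to change.** In SAP 8.7, for the Day 28 analysis only:

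1. Censor patients who die before Day 14, and those who die unresolved from Day 14 up to Day 28, at one day past Day 28 (Day 29). Include death on Day 14 itself.
2. Keep the existing rule that resolution before a death after Day 14 counts as a success.
3. State whether resolution followed by death before Day 14 counts in this analysis.
4. Say that event times use nominal visit days. Protocol 4.3.9 schedules the last assessment at Day 29 with a window of two further days, so if actual dates are used the censoring day must fall after that window.

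An alternative is to report the cumulative incidence of resolution with death as a competing event (Aalen-Johansen, with Gray's test). That counts resolution before any death as an event, so it is a different endpoint. It should not be presented as equivalent to treating every death by Day 28 as never resolved, which would also overturn the rule in item 2.

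The cost is a few sentences and a small programming change, with no new data and no effect on the Day 14 tables.
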